10.4 SAE reporting in FREMS-PDPN

For all SAEs, the PI or delegate must do one of the following:

1. **Record safety reporting-exempt SAEs** in the medical notes but **not report** them to the Trial Office on an SAE form as per Section 10.4.1.
2. **Report SAEs to the trial office in a non-expedited manner.** This can only be done for the pre-defined subset of SAEs as per Section 10.4.2.
3. **Report SAEs to the trial office in an expedited manner.** All SAEs not covered by the above 2 categories must be reported within 24 hours of the site research team becoming aware of the event.

Note: when an SAE occurs at the same hospital at which the participant is receiving trial intervention or is being followed up for trial purposes, processes must be in place to make the trial team at the hospital aware of any SAEs, regardless of which department first becomes aware of the event, in an expedited manner.

10.4.1 SAEs not requiring reporting to the Trial Office

At whatever time they occur during an individual's participation, during the AE reporting period, the following are not considered to be critical to evaluations of the safety of the trial:

- Pre-planned hospitalisation
- Hospital admissions lasting less than 24 hours

All events which meet the definition of serious must be recorded in the participant notes, including the causality and severity, throughout the participant's time on trial, including follow-up, but for trial purposes these events do not require reporting on the SAE Form. Such events are "safety reporting exempt".

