10. ADVERSE EVENTS REPORTING

10.1 Definitions

Table 6: Adverse event reporting definitions

Severity Definitions	Mild	Awareness of signs or symptoms that do not interfere with the participant’s usual activity or are transient and resolved without treatment and with no sequelae.
	Moderate	A sign or symptom, which interferes with the participant’s usual activity.
	Severe	Incapacity with inability to do work or perform usual activities.
Adverse Event	AE	Any untoward medical occurrence in a participant participating in the trial which does not necessarily have a causal relationship with the intervention received.
Related Event	RE	An event which resulted from the administration of any of the research procedures.
Serious Adverse Event	SAE	An untoward occurrence that: Results in death Is life-threatening* Requires hospitalisation or prolongation of existing hospitalisation Results in persistent or significant disability or incapacity Consists of a congenital anomaly/ birth defect

		Or is otherwise considered medically significant by the Investigator**
Unexpected Event	UE	The type of event that is not listed in the protocol as an expected occurrence.
Related and Unexpected Serious Adverse Event	N/A	A SAE that meets both the definition of a Related and Unexpected Event.

* The term *life-threatening* is defined as diseases or conditions where the likelihood of death is high unless the course of the disease is interrupted.

** Medical events that may not be immediately life-threatening or result in death or hospitalisation but may jeopardise the participant or may require intervention to prevent one of the other outcomes listed in the definitions above.

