10.4.2 SAEs requiring non-expedited reporting to the Trial Office

Where the safety profile is well established, the causal relationship between the intervention (or the participant's underlying condition) and the SAE may be known. That is, such events are protocol-defined as "expected" (see Section 10.7 Assessment of expectedness of an SAE by the CI).

Such events should still be recorded by the trial team in the participant's notes and reported to the Trial Office on the trial specific SAE form but do not require expedited reporting (immediately on the site becoming aware of the event) since the assessment of expectedness for the specified events has been pre-defined. It is expected that these SAEs are reported within 7 days of the site becoming aware of the event. These include:

- Hospitalisations related to DM or other pre-existing conditions

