10.7 Assessment of expectedness of an SAE by the CI

The CI or delegate will assess related SAEs for expectedness with reference to the criteria in **Table 8**.

Table 8: Categories of expectedness

Category	Definition
Expected	An adverse event that is consistent with known information about the trial related procedures, trial intervention (as described in the manufacturer's guidance) or pre-existing conditions of the participant (including DM).
Unexpected	An adverse event that is not consistent with known information about the trial related procedures, trial intervention, or pre-existing conditions of the participant.

If the event is unexpected (i.e. it is not defined in the protocol as an expected event) it will be classified as a related and unexpected SAE.

The CI will undertake review of all SAEs and may request further information from the clinical team at site for any given event to assist in this.

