10.9 Reporting SAEs to third parties

The independent Data Monitoring Committee (DMC) may review any SAEs at their meetings.

The Trial Office will submit a progress report to the Research Ethics Committee (REC) and University of Birmingham (UoB) Research Governance Team (RGT) annually starting 12 months after the date of the favourable opinion was given. An electronic copy should be emailed to the REC within 30 days of the end of the reporting period.

The Trial Office will report all events categorised as Unexpected and Related SAEs to the REC and RGT within 15 days of being notified.

Details of all Unexpected and Related SAEs and any other safety issue which arises during the course of the trial will be reported to the PIs. A copy of any such correspondence should be filed in the ISF and Trial Master File (TMF).

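### The unqualified under-24-hour exemption keeps treatment-related short admissions from central SAE review, and pre-defined expectedness keeps related diabetes hospitalisations from the 15-day ethics report

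*Protocol*

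**What the plan says.** Section 10.1 (Table 6) makes an event serious if, among other criteria, it "Requires hospitalisation or prolongation of existing hospitalisation", with no minimum stay. Section 10.3 lists SAEs, without exception, as reported on the SAE form.

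Section 10.4 then sets up three routes:

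- **Exempt (10.4.1).** Planned admissions and "Hospital admissions lasting less than 24 hours" are covered because "the following are not considered to be critical to evaluations of the safety of the trial". The consequence is that "for trial purposes these events do not require reporting on the SAE Form". The site still has a duty: "All events which meet the definition of serious must be recorded in the participant notes, including the causality and severity". Section 10.6 asks for the Table 7 causality categories to be used in that source record.
- **Non-expedited (10.4.2).** "Hospitalisations related to DM or other pre-existing conditions" go on the SAE form within 7 days, with expectedness fixed in advance.
- **Expedited (10.4.3).** Everything else goes on the SAE form within 24 hours.

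Downstream, 10.6 has the Trial Office pass each SAE form it receives to the CI for independent causality review. Section 10.7 states "The CI will undertake review of all SAEs", and its Table 8 counts consistency with pre-existing conditions, diabetes included, as expected. Section 10.9 says "The Trial Office will report all events categorised as Unexpected and Related SAEs to the REC and RGT within 15 days" of being notified.

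**The concern.** The exemption turns on length of stay alone. A short admission that the site itself attributes to the stimulation is handled in the same way as one with an obvious unrelated cause, and nobody outside the site has to be told on an SAE form. The second rule has a related weakness. Every participant has diabetes and neuropathy, so an admission for worsening neuropathy or a foot problem that was judged related to treatment could still be expected by definition.

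Two things are at stake. Related SAEs can miss the people charged with assessing them, in a trial where section 6.6 rules out unblinding and so leans on central oversight. And the frequency of SAEs, a stated safety outcome in 8.4.2, is incomplete by rule, as are the SAE data available to the Data Monitoring Committee.

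**Working it through.** No calculation is needed to test the rule; it can be followed through sections 10.3 to 10.9 for three kinds of event.

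| Step | (a) Related admission under 24 h | (b) Related hospitalisation of 24 h or more, linked to diabetes or a pre-existing condition | (c) Any other SAE |
|---|---|---|---|
| Causality recorded by site | Yes, in the notes (10.4.1, 10.6) | Yes | Yes |
| SAE form to Trial Office | No (10.4.1) | Yes, within 7 days (10.4.2) | Yes, within 24 h (10.4.3) |
| Independent CI causality review (10.6) | No, because it starts on receipt of the form | Yes | Yes |
| Case-by-case expectedness (10.7) | No | No, pre-defined as expected | Yes, if related |
| 15-day REC/RGT report (10.9) | No, because there is no notification | No, because it is not classed unexpected | Yes, if related and unexpected |
| AE log (10.3) | Arguably, in a limited window | Not the relevant route | Not the relevant route |

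**Column (a) against the general wording.** Section 10.3 lists SAEs as reported and 10.7 has the CI reviewing all of them. Under 10.4.1 neither is true of a short admission.

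**How far the AE log helps in column (a).** Ten sessions on consecutive working days span 12 calendar days from a Monday start and 14 from a later weekday. Adding 7 days gives 12 + 7 = 19 to 14 + 7 = 21 days, about 3 weeks. AE reporting runs to the end of follow-up at 6 months, about 26 weeks from randomisation, so the log is closed for roughly 26 − 3 = 23 of those weeks. (This assumes a prompt start and no missed sessions.) Within its window the log is worded for events possibly or definitely related and leaves out 'probably', which Table 7 also counts as related.

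**Column (b) against the stated risk.** Section 6.6 names soreness at the patches as the only risk of either intervention. On that statement, a hospitalisation caused by the intervention would not be a known effect. Under 10.4.2 and Table 8 the same event becomes expected once it is linked to a pre-existing condition. The pre-label is not confined to diabetes; it covers any pre-existing condition.

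**The case against.** The strongest reply is that this is a reasoned choice. Section 10.3 argues for targeted reporting on the ground that the safety profile is well known, section 3.2 rates the trial as no riskier than ordinary care, and the device is CE marked. Section 10.4 openly creates an exempt tier, so the reference in 10.7 to all SAEs can be read as all those reported. The 15 days in 10.9 run from notification, so an exempt event breaches no deadline. The AE log covers the period in which section 6.6 expects device effects. Sensory testing and the neuropathy score in selected centres look for worsening neuropathy independently of SAE labels.

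Much of this stands. Exempting planned or brief admissions is not wrong in itself, and the clash with 10.3 and 10.7 is one of wording to be reconciled. But none of it gives a reason to exempt an event the site considers related, and the AE log leads to no CI or REC step.

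Four stronger readings are tempting and are not supported:

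- *That diabetes-related hospitalisations escape causality review.* They do not. They go on the SAE form and to the CI, and 10.6 treats an SAE as related if either the site investigator or the CI judges it so.
- *That short related admissions are invisible or unassessed.* The site must record causality and severity, and the AE log may capture them early on.
- *That life-threatening events are plainly exempt if the stay is short.* The exempt item is the admission. The text neither says this nor rules it out, which is a reason to clarify it.
- *That the comparison of arms is biased.* The rule is identical in both blinded arms. It lowers the SAE count, but nothing in the protocol shows a difference between arms.

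**Conclusion.** The point holds in two parts of different weight. First, because the under-24-hour exemption has no relatedness or seriousness condition, a related short admission misses independent causality review, expectedness assessment and 15-day reporting, and drops out of the SAE outcome. Second, and more narrowly, pre-defined expectedness means that a related hospitalisation linked to diabetes or another pre-existing condition misses only individual expectedness assessment and the 15-day report.

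This rests on a literal reading of 10.4.1 and on 10.6 and 10.9 operating only once the Trial Office has been told. The number of events affected cannot be given, because the protocol states no SAE rate; it may well be small. The case for change is that the rule sends related SAEs down the wrong route and is cheap to correct.

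**What to change.** - **10.4.1:** limit the exemption to events judged 'unlikely' or 'not related' that meet no other seriousness criterion.
- **10.4.2:** limit the non-expedited, pre-defined-expected route to events judged unrelated.
- **Table 8:** assess the expectedness of a related SAE against the known effects of the intervention and trial procedures, not against the participant's underlying conditions.
- **10.3, 10.7 and 10.9:** align the wording with the amended routes, so that the scope of reporting and of CI review is the same throughout, and add 'probably' to the AE-log criterion.

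The cost is a short protocol amendment and a few extra SAE forms. Sample size, visits and analysis are unaffected.

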10.4.2 SAEs requiring non-expedited reporting to the Trial Office

Where the safety profile is well established, the causal relationship between the intervention (or the participant's underlying condition) and the SAE may be known. That is, such events are protocol-defined as "expected" (see Section 10.7 Assessment of expectedness of an SAE by the CI).

Such events should still be recorded by the trial team in the participant's notes and reported to the Trial Office on the trial specific SAE form but do not require expedited reporting (immediately on the site becoming aware of the event) since the assessment of expectedness for the specified events has been pre-defined. It is expected that these SAEs are reported within 7 days of the site becoming aware of the event. These include:

- Hospitalisations related to DM or other pre-existing conditions

10.4.3 SAEs requiring expedited reporting to the Trial Office

All SAEs not listed in Sections 0 and 10.4.2 must be reported to the Trial Office on the trial specific SAE form within 24 hours of the site research team becoming aware of the event.

10.5 SAE Reporting process

On becoming aware that a participant has experienced an SAE which requires reporting on an SAE form, the PI or delegate should report the SAE to their own Trust in accordance with local practice and to the Trial Office.

To report an SAE to the Trial Office, the PI or delegate must complete, date and sign the trial specific SAE form. The completed form together with any other relevant, appropriately anonymised, data should be submitted to the Trial Office using the information below in accordance with the timelines given in Section 10.4.2 and 10.4.3.

To report an SAE, submit the SAE Form to:

www.fremspdnpn.bctu.bham.ac.uk

Where an SAE Form has been completed by someone other than the PI initially, the original SAE form must be countersigned by the PI to confirm agreement with the causality and severity assessments.

On receipt of an SAE form, the Trial Office will allocate each SAE a unique reference number and notify the site via email to the site as proof of receipt. The site and the Trial Office should ensure that the SAE reference number is quoted on all correspondence and follow-up reports regarding the SAE and filed with the SAE in the ISF.

If the site has not received confirmation of receipt of the SAE or if the SAE has not been assigned a unique SAE identification number within 1 working day of reporting, the site should contact the Trial Office.

10.6 Assessment of causality of an SAE

When completing the SAE form, the PI (or, throughout this section, a medically qualified delegate) will be asked to define the nature of the seriousness and causality (relatedness; see Table 7: Categories of causality) of the event.

In defining the causality the PI must consider if any concomitant events or medications may have contributed to the event and, where this is so, these events or medications should be reported on the SAE form. It is not necessary to report concomitant events or medications which did not contribute to the event.

As per **Table 7**, all events considered to be ‘possibly’, ‘probably’, or ‘definitely’ related to the intervention will be reported by the Trial Office as ‘related’; all events considered at site to be ‘unlikely’ or ‘unrelated’ to the intervention will be reported by the Trial Office as ‘unrelated’. The same categorisation should be used when describing AEs and protocol-exempt SAEs in the source data.

Table 7: Categories of causality

Category	Definition	Causality
Definitely	There is clear evidence to suggest a causal relationship, and other possible contributing factors can be ruled out.	Related
Probably	There is evidence to suggest a causal relationship, and the influence of other factors is unlikely.	
Possibly	There is some evidence to suggest a causal relationship. However, the influence of other factors may have contributed to the event (e.g. the participant’s clinical condition, other concomitant events or medication)	
Unlikely	There is little evidence to suggest there is a causal relationship. There is another reasonable explanation for the event (e.g. the participant’s clinical condition, other concomitant events or medication).	Unrelated
Not related	There is no evidence of any causal relationship.	

On receipt of an SAE Form, the Trial Office will forward it, with the unique reference number, to the Chief Investigator (CI) or delegate who will independently* review the causality of the SAE. An SAE judged by the PI or CI or delegate to have a reasonable causal relationship (“Related” as per **Table 7:** Categories of causality) with the intervention will be regarded as a related SAE. The severity and causality assessment given by the PI will not be downgraded by the CI or delegate. If the CI or delegate disagrees with the PI’s causality assessment, the opinion of both parties will be documented, and where the event requires further reporting, the opinion will be provided with the report.

*Where the CI is also the reporting PI an independent clinical causality review will be performed.

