10.2 Adverse event recording – general

The recording and reporting of Adverse Events (AEs) will be in accordance with the UK Policy Framework for Health and Social Care Research, the Principles of GCP as set out in the UK Statutory Instrument (2004/1031; and subsequent amendments) and the requirements of the Health Research Authority (HRA). Definitions for adverse event reporting are listed in **Table 6: Adverse event reporting definitions** in Section 10.1.

It is routine practice to record AEs in the participant's medical notes and it is also recommended that this includes the documentation of the assessment of severity and seriousness and also of causality (relatedness) in relation to the intervention(s) in accordance with the protocol.

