10.3 AE reporting in FREMS-PDPN

The reporting period for AEs in FREMS-PDPN will be from the start of treatment until the end of trial follow-up.

The safety profile for this trial population and interventions are well characterised so a strategy of targeted reporting of AEs will not affect the safety of participants. Only those AEs detailed below will be reported:

- Serious Adverse Events (SAEs) (reported on trial specific SAE CRF).
- AEs possibly or definitely related to trial treatment, occurring between the start of trial treatment and 7 days after the end of the trial treatment period (reported on trial specific AE log).

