15.2 Model-based economic evaluation

In order to assess the long-term cost-effectiveness of FREMS over the lifetime of the patient, a model-based economic evaluation will be conducted. The model will be populated with data (costs, utilities etc.) from various sources, including data obtained from the RCT, literature reviews and expert opinions. A Markov model will be used to estimate the lifetime cost-effectiveness of FREMS. Incremental cost-effectiveness ratios will be estimated and a cost-effectiveness plane as well as a cost-effectiveness acceptability curve constructed. Deterministic and probabilistic sensitivity analysis will be used to assess the robustness of the results obtained from the model.

16.SUBSTUDY

Based on recommendations by the European Medicine Agency for the design of drug trials in chronic neuropathic pain conditions, this trial includes an explorative sub-study to allow stratification according to stimulus evoked pain [49].

Quantitative sensory testing (QST) according to the German Network for Neuropathic pain will assess detection and pain threshold for a variety of sensory qualities [67]. A gain or loss of function can then be determined by calculating z-scores based on values from the normal population. Presence or absence of plasticity changes like central wind-up will also be assessed with the assessment of temporal summation (increased pain to repeated stimuli). We expect to recruit up to 100 patients between Sheffield and Liverpool providing QST data at baseline which can be used to identify a preferential profile for responders to the FREMS treatment [76]. QST will also be able to determine any meaningful recovery or worsening of sensory function 3 months after treatment as a correlate for the safety of the treatment in patients with an underlying neuropathy.

QST is a non-invasive methodology used to assess a patient's somatosensory system function in peripheral neuropathic pain. In this study, QST will be performed following the standardised protocol of the German Research Network on Neuropathic Pain, exploring 11 sensory modalities. It will be performed by the technician trained according to the standards defined by the German Network using equipment already owned by the Trust. The time required for a complete QST is expected to be about

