16.1 Sensory testing protocol

A formal standardised QST protocol will be performed according to the German Research Network on Neuropathic Pain protocol. This battery of tests has been extensively validated and has age and gender at birth specific normative ranges. All tests will be performed on a single leg with the same leg used for both baseline and follow up assessments. The testing protocol has the following components:

Thermal Sensations

The tests for thermal sensations will be performed using a TSA 2001-II (MEDOC, Israel) thermal sensory testing device. All thresholds will be obtained with ramped stimuli (1 °C/s) that will be terminated when the subject presses a button. Cut-off temperatures are 0 and 50 °C. The baseline temperature is 32 °C. Cold detection threshold and warm detection threshold will be measured as the threshold temperature able to elicit, respectively, a sensation of cold or warm. Similarly, cold pain threshold, and heat pain threshold will be measured as the threshold temperature able to elicit a painful or distressing cold or warm sensation. For each modality, the mean threshold temperature of three consecutive measurements will be calculated. Later, the thermal sensory limen procedure, consisting of six alternating cold and warm stimuli, will be carried out. The mean temperature span for sensation change and the number of paradoxical heat sensations during the cold stimuli will be recorded.

Mechanical detection threshold (MDT)

This will be measured with a standardised set of modified von Frey hairs (Opti-hair2-Set, Marstock Nervtest, Germany) that exert forces upon bending between 0.25 and 512 mN graded by a factor of 2 (1– 2 s contact time). The contact area of the von Frey hairs with the skin is of uniform size and shape (rounded tip, 0.5 mm in diameter) to avoid sharp edges that would facilitate nociceptor activation. Using the “method of limits”, five threshold determinations will be made, each with a series of ascending and descending stimulus intensities. The final threshold was the geometric mean of these five series.

Mechanical pain threshold (MPT)

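### Table 6 counts an event caused by any research procedure as related, but the working causality rules test only the intervention, and SAE reporting opens after baseline sensory testing

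*Protocol*

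**What the plan says.** Two places in the protocol take the wide view of relatedness. Table 6 in section 10.1 describes a Related Event as "An event which resulted from the administration of any of the research procedures". Table 8 in section 10.7 judges expectedness against what is known of trial procedures as well as of the intervention.

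The rules that sites and the Chief Investigator (CI) apply are narrower:

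- Section 10.2 recommends that the medical notes document "causality (relatedness) in relation to the intervention(s) in accordance with the protocol".
- Section 10.3 limits non-serious AE reporting to events related to trial treatment, from its start until 7 days after it ends.
- Section 10.6 says that events judged possibly, probably or definitely "related to the intervention will be reported by the Trial Office as" related, and that the remaining categories are reported as unrelated. It adds: "The same categorisation should be used when describing AEs and protocol-exempt SAEs in the source data".
- The CI review in section 10.6 says that an SAE which either the site or the CI considers plausibly caused has its link tested "with the intervention will be regarded as a related SAE".

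On timing, section 10.3 says: "The reporting period for AEs in FREMS-PDPN will be from the start of treatment until the end of trial follow-up".

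The trial includes a research-only procedure, QST. Section 16 says: "We expect to recruit up to 100 patients between Sheffield and Liverpool providing QST data at baseline". Section 16.1 describes thermal ramps that stop on a button press ("Cut-off temperatures are 0 and 50 °C"), weighted pinpricks up to 512 mN, and pressure up to about 1000 kPa.

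**The concern.** QST serves partly as a safety check on the interventions, and it is applied to legs with confirmed neuropathy. It is a research procedure but not the intervention. An injury caused by it is therefore related by the definition in Table 6 and unrelated by the rule in section 10.6. Two sites could label the same injury differently, each with support from the text.

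The label has consequences. Under section 10.7 only related SAEs are assessed for expectedness. Under section 10.9 only SAEs that are both related and unexpected go to the Research Ethics Committee (REC) and Research Governance Team (RGT) within 15 days. A separate gap arises because the reporting period opens at first treatment, whereas baseline QST belongs to the visit before it.

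**Working it through.** The protocol gives no figure to reproduce here. The check sets the definitions beside the operative rules and follows a QST-caused event through them.

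**What relatedness is measured against**

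| Place | Reference for causality |
|---|---|
| Table 6 (10.1) | any research procedure |
| Table 8 (10.7), expectedness | trial procedures, the intervention, pre-existing conditions |
| 10.2, recording in notes | the intervention(s) |
| 10.3, non-serious AEs | trial treatment |
| 10.6, site assessment | the intervention |
| 10.6, CI review | the intervention |

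Section 10.7 sends only related SAEs to the expectedness step. If section 10.6 is followed, procedure-caused SAEs have been screened out before the reference to procedures in Table 8 can apply.

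**Following an event through the rules**

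1. *Serious injury at the 3- or 6-month QST.* This falls inside the reporting period. It goes to the Trial Office on the SAE form unless it is exempt under 10.4.1 (a pre-planned hospitalisation, or an admission under 24 hours), and the CI reviews it. Under 10.6 it is labelled unrelated, because the intervention did not cause it. It then receives no expectedness assessment (10.7) and no 15-day REC/RGT report (10.9). Under Table 6 it is a Related Event.

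2. *Serious event after baseline QST and before first treatment.* Table 5 places baseline QST at visit 0, and the reporting period opens at the start of treatment. Section 10.4.1 requires serious events to be recorded in the notes throughout the participant's time on trial, but no report to the Trial Office is required before that period opens. The same holds for any SAE between randomisation and first treatment. Section 7.1 expects treatment on the day of randomisation but allows up to 7 days.

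3. *Non-serious injury from QST.* On schedule, the window closes at most about 7 (delay to start) + 14 (ten working days) + 7 (days after treatment) = 28 days after randomisation. The 3-month QST comes at about 90 days, and baseline QST precedes the window. No scheduled QST session falls inside it, so these events are not reportable.

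**Exposure**

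Section 3.1 and Table 5 schedule QST at baseline, 3 months and 6 months; section 8.5 lists baseline and 3 months only. With up to 100 participants:

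- three sessions each: 100 × 3 = 300 sessions;
- two sessions each: 100 × 2 = 200 sessions;
- baseline sessions: up to 100; later sessions: 100 to 200.

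**The case against.** A reader might infer that harm from QST cannot be reported as related at all, and that the REC, RGT and Data Monitoring Committee (DMC) could not act on it. The text does not support that. Section 10.2 names Table 6 as the source of the adverse event definitions, and Table 6 builds its category of related and unexpected SAE on the wide definition. Section 10.9 sends every event in that category to the REC and RGT. The individual category definitions in Table 7 speak of a causal relationship without naming the intervention. A route to a related report therefore exists, and section 10.6 conflicts with it. The fair description is a contradiction.

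Visibility is also better than the strong reading suggests. Once treatment has started, non-exempt SAEs reach the Trial Office whatever their cause, the CI reviews all SAEs, and the DMC may review any of them and can meet in an emergency. What is lost at 3 and 6 months is the related label and the steps that depend on it. Serious events before treatment must still be written in the notes.

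The absence of non-serious QST injuries from reporting (case 3) follows largely from the targeted-reporting strategy stated in section 10.3, alongside a risk assessment in section 3.2 of no more than standard medical care. That is a design choice and is not counted here as an error.

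What remains is the conflict between Table 6 and section 10.6, and the unreported interval before first treatment.

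**Conclusion.** The point holds as an internal contradiction with a timing gap attached. Sections 10.2, 10.3 and 10.6, including the CI review, are narrower than Tables 6 and 8. Following section 10.6 literally would mislabel a serious QST-caused injury and withhold the two steps that depend on the label. SAEs after baseline QST, or otherwise between randomisation and first treatment, need not be reported to the Trial Office.

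The practical size is probably modest. QST is confined to two centres and up to 100 participants, and section 16 calls it non-invasive. Visits 0 and 1 are expected to be combined in most cases, so the pre-treatment interval will usually be short. The 200 to 300 sessions measure exposure; a reader might take them as a measure of harm, but the protocol gives no injury rate and none can be derived. No efficacy analysis is affected.

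The conclusion assumes that baseline QST is done before the first treatment session, as its place at visit 0 implies, and that sites apply section 10.6 as written.

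**What to change.** - In sections 10.2, 10.3 and 10.6, including the CI review, replace the references to the intervention or trial treatment with: trial intervention or any research procedure, including QST. This brings the operative rules into line with Tables 6 and 8.
- Add a tick box to the SAE form showing whether the suspected cause is the intervention or a research procedure.
- Start the SAE reporting period at main-trial consent, before baseline QST. This also closes the interval of up to 7 days between randomisation and first treatment.

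The change to 10.3 alone would not bring scheduled QST sessions into the non-serious AE window. A separate window for them would be an optional extension of the targeted strategy and is not needed to resolve the contradiction.

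The cost is a protocol wording change, one extra field on a form, a slightly longer SAE window and a few more entries.
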